14.1.1 Primary Objective: Analysis of the primary endpoints

The primary objective is to assess the HRQoL through the MSQoL-54 scale in highly active RMS subjects treated with Mavenclad® for 2 years (24 months).

The primary endpoints for the study are the changes in HRQoL assessed by MSQoL-54 physical health and mental health at 24 months post-Baseline assessment. Differences in MSQoL-54 scores between measurements at the Month 24 Visit and Baseline will be assessed using repeated mixed-effects linear regression, accounting for clinically relevant factors, within subject correlation and within pooled center correlation.

As the analysis set concerns repeated measurements for outcomes for each individual, it is likely that observations pertaining to each individual will be correlated. Furthermore, as this is a multi-center study, it is likely that clustering of individuals within study sites will produce an additional source of correlation. Mixed-effects regression, whereby a three-level hierarchical model is specified for observations within subjects within-pooled centers, will be used to account for within-subject and within-pooled center correlation (Gibbons et al., 2010).

The analysis will also adjust for factors deemed to be prognostic for the primary endpoint, as judged by clinical experts. These factors are the age and EDSS at Baseline, (see Section 9 for details).

The primary endpoints are the changes from Baseline to Month 24 Visit in Physical and Mental health composite of the MSQoL-54. They will be analyzed with a repeated mixed-effects linear model for change from Baseline that will take all planned intermediate measurements into account whereby a three-level (visits within subjects within centers) hierarchical model is specified for repeated MSQoL-54 Physical or Mental health composite scores.

$$Y = X\beta + \gamma + e, \text{ where}$$

Y represents change from baseline in MSQoL score,

X represents values of fixed effects including MSQoL score, age and EDSS at Baseline, and Visit (defined as a class variable),

β represents set of regression coefficients,

γ represents pooled center random effect,

e represents a random error, potentially correlated for different visits within a subject (nested within a center).

The LS Means will be calculated with observed margin which reflects the distribution of age, ~~g~~ categories at Baseline and respective Baseline composite score of the FAS. An unstructured covariance matrix will be assumed for the model. If the model doesn't converge a variance components covariance structure will be used instead or the center effect will be specified as a fixed effect instead (same model as specified as a sensitivity analysis below).

The following hypotheses will be evaluated exploratively:

$$H_{01}: \Delta_{\text{Physical Health}} = 0 \text{ vs. } H_{11}: \Delta_{\text{Physical Health}} \neq 0$$

$$H_{02}: \Delta_{\text{Mental Health}} = 0 \text{ vs. } H_{12}: \Delta_{\text{Mental Health}} \neq 0,$$

where $\Delta = EY$ denotes the population mean change of the respective score.

The study is exploratory in nature. A control of the potential type-I-error inflation caused by multiple endpoints and multiple testing is not implemented.

Analysis (Analysis Set)	Derivation	Statistical Analysis Methods	Missing data handling
Primary endpoint: Changes in MSQoL-54 physical and mental health composite scores from Baseline to Month 24			
Primary (FAS)	Changes from Baseline in physical health composite (MSQoL-54) to the Month 12 Visit and Month 24 Visit	Repeated mixed-effects linear model with the following adjusting factors: 
• Baseline score,• Age (years),• EDSS (≤ 3, > 3),• Visit,• Within-pooled center correlations,• Within-subject correlation. Estimated Least Square Means (LS Means) and corresponding Standard Errors (SE) will be presented by Visit including 2-sided p-values and 95% CI that are not adjusted for multiple testing due to the exploratory nature of the study.	Missings at Baseline: Subjects with a missing MSQoL assessment at Baseline will not be included in the repeated mixed-effect linear model analysis. Missing covariate or stratification information will be imputed as specified in Section 9. Missing post-Baseline observations: Missing post-Baseline assessments will not be imputed. The repeated measurement model handles missing post-Baseline assessments under the assumption of missing at random. Missing Sexual function scores: See below.
Primary (FAS)	Changes from Baseline in mental health composite (MSQoL-54) to the Month 12 Visit and Month 24 Visit		

Handling of missing scores in sexual function:

The MSQoL-54 questionnaire has been set-up to allow only skipping of questions 46 - 49 about the Sexual function by selecting “Not applicable” as an answer. If more than one question in this part was answered, the Sexual function score will be calculated according to the scoring manual (Vickrey 1995), i.e. the mean of the answered questions will be used as score. If only one or no question was answered, the Sexual function score will be imputed with the answer of the Satisfaction with sexual function score.

CCI

CCI

14.2 Secondary Endpoint: Treatment global satisfaction assessed by TSQM v1.4 at Month 6 Visit (Interim Analysis)

The TSQM v1.4 questionnaire is a generic questionnaire to test treatment satisfaction with domains in Effectiveness, Side Effects, Convenience and Global Satisfaction and has previously been used in MS subjects (Vermersch et al., 2014). The scores will be derived according to the TSQM User Manual Version 1.0. The TSQM v1.4v scores range from 0% to 100%, with 100% being the best possible score.

At the Interim analysis, the Global Satisfaction score at Month 6 Visit will be analyzed without taking the later observations into account. At the final analysis, the Month 6 Visit will be analyzed as tertiary endpoint in a repeated model that includes the Month 12 and 24 Visit (see Section 14.3.2).

Global Satisfaction at Month 6 Visit will be analyzed at the interim analysis with a mixed linear model. The model will be adjusted for age (in years), EDSS at Baseline (≤ 3 , > 3) and within-pooled center correlations. An unstructured covariance matrix will be assumed for the model. If the model doesn't converge a variance components covariance structure will be used instead.

CCI

CCI

CCI

CCI

CCI

[figure not shown]
CCI

CCI

CCI

CCI

CCI

All volume changes will be listed by subjects.

CCI

CCI

CCI

CCI

CCI

CCI

CCI

CCI

15 Safety Analyses

The subsections in this section include specifications for summarizing safety endpoints that are common across clinical studies such as adverse events, laboratory tests and vital signs.

Safety analyses will be done on the SAF. Unless otherwise specified, the safety analysis will be done for interim and final analysis.

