8.5.1 General Considerations

The study is exploratory in nature. A control of the potential type-I-error inflation caused by multiple endpoints and multiple testing is not implemented.

For analysis of all endpoints, differences with a p-value of 0.05 or less will be considered nominally statistically significant. Parameter estimates with associated 95% confidence intervals will be reported in each analysis.

Subjects' demographic factors and Baseline clinical characteristics will be summarized with the following measures: mean with standard deviation, minimum and maximum for normally distributed continuous variables, median with interquartile range, minimum and maximum for other continuous variables and counts with percentages for categorical variables.

As the analysis set concerns repeated measurements for outcomes for each individual, it is likely that observations pertaining to each individual will be correlated. Furthermore, as this is a multi-centre trial, it is likely that clustering of individuals within trial sites will produce an additional source of correlation. Mixed-effects regression, whereby a three-level hierarchical model is specified for

observations within subjects within trial sites, will be used to account for within-subject and within-centre correlation (Gibbons et al., 2010).

Assessment schedules

It is likely that the 2nd year treatment may be delayed substantially for a small number of subjects for whom the second dose is not required immediately. Due to the need for a finite follow-up period, a buffer of 3 months is given for subjects who do not receive the second treatment at the specified time. Subjects for whom treatment is delayed by over 3 months may not have all assessment data captured and as such, these observations will be treated as missing.

In each analysis, should assessment be delayed, subjects' assessment data will be treated as though it occurred at the time point specified and inferences will be conducted accordingly.

Missing data

Should missing data be present in Baseline covariates included in the analysis models, mean or median imputation and use of a missing indicator will be used for continuous and categorical covariates, respectively.

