Unless otherwise specified in respective sections, missing data will not be replaced.

The handling of missing covariate and stratification factor information is described below.

The handling of missing DMD end date is described in Section 12.

Incomplete or missing onset dates of relapses from “MS Relapse Report” will be imputed as follows:

- In cases where the onset date is completely or partially missing but the onset month and year, or the onset year are equal to the start of study medication then the onset date will be replaced by the start date of study medication.
- In all other cases the missing onset day or missing onset month will be replaced by 1.

In all subject data listings, imputed values will be presented. In all listings imputed information will be flagged.

Missing statistics, e.g. when they cannot be calculated, should be presented as “nd”. For example, if n=1, the measure of variability (e.g. SD) cannot be computed and should be presented as “nd”.

Where tables are presented over time, the total of missing and non-missing observations at each time-point should reflect the population still in the study at that time. This does not apply when imputations are made beyond study withdrawal.

Data Handling in case of major PDs

Electronic Patient Reported Outcomes (ePRO) assessments performed completely in non-native language will not be used for the statistical summaries or analyses as planned in this IAP and will be flagged accordingly in any listings.

Any other PD will not be considered in the planned statistical analyses.

Covariates and stratification factors

- Age

Age (years) at time of Informed Consent (loaded from iRT). Missing age will be replaced as follows if used as a covariate:

1. Age will be estimated from the year of birth (year of IC – year of birth), as recorded in the electronic Case Report Form (eCRF)
2. If year of birth is missing, age will be imputed by the mean age of the FAS.

- **Pooled centers**

Some centers will have few eligible subjects only. Therefore, the centers will be pooled together in geographical groups by country and the Scandinavian countries will be further pooled together to one Scandinavian pool.

Software(s)

All analyses will be performed using SAS® Software version 9.3 or higher.

10 Trial Participants

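### When pooled center is made a fixed effect, the MSQoL-54 model has no term left for clustering by study site, so its intervals are too narrow if sites differ

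*SAP*

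**What the plan says.** Protocol 8.5.1 expects correlation within trial sites and specifies a three-level model for "observations within subjects within trial sites". Protocol 8.5.2 and the synopsis are looser: they speak of correlation within centre or region, and 8.5.2 refers back to 8.5.1 for details.

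SAP 14.1.1 keeps the premise, stating that "it is likely that clustering of individuals within study sites will produce an additional source of correlation". Its next sentence sets the levels: "Mixed-effects regression, whereby a three-level hierarchical model is specified for observations within subjects within-pooled centers". The model it then writes down has one term above the subject: "γ represents pooled center random effect". SAP Section 9 (Covariates and stratification factors) defines that term. Because some centers will have few subjects, "the centers will be pooled together in geographical groups by country and the Scandinavian countries will be further pooled together to one Scandinavian pool".

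If the primary model does not converge, SAP 14.1.1 offers two alternatives without ranking them: a variance components structure, or "the center effect will be specified as a fixed effect instead". It adds that the second is the same model as the sensitivity analysis, whose own text is redacted.

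SAP 7, which lists changes from the protocol's analyses, covers the delayed second course, the 1-year interim analysis and COVID-19. It does not mention the move from site to pooled center.

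**The concern.** The SAP names study site as the level at which outcomes are correlated, and no term in the visible model sits at that level. With a random pool effect, the estimated pool variance picks up much of what sites contribute, because each pool mean averages only a handful of sites. With a fixed pool effect, that route closes. The within-subject covariance matrix still links a subject's visits, but two subjects at the same site and visit are treated as independent once their country is accounted for.

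The fixed-center version matters in two ways. It can supply the primary result if the random-effects model fails to converge, and it appears to be the check set beside the primary result. Either way, its interval for the Month 24 change would claim more precision than the design gives. For a sensitivity analysis, that risks false reassurance.

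The reason given for pooling is a reason not to fit some 120 fixed site effects. It is not a reason against a random site intercept or a site-clustered standard error, since both tolerate small sites.

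**Working it through.** The protocol's sample-size section and statistics appendix are not in the public copy, so no planned SD, power or ICC can be reproduced. The check does not need them.

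**Inputs.** 445 subjects (Protocol synopsis). About 120 sites (Protocol Section 2). 19 listed countries, of which four are Scandinavian (SAP 11.1), so 19 − 4 + 1 = 16 pools. Mean site size m = 445/120 = 3.71; sites per pool 120/16 = 7.5; subjects per pool 445/16 = 27.8. Two-sided 95% intervals (SAP 9). Site ICC and the coefficient of variation (CV) of site size are assumed, because the documents give neither.

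**Formula.** With fixed pools and LS means at observed margins, the model SE of the mean change is about s/√N. The true SE is larger by √DE, where

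DE = 1 + [(1 + CV²)·m − 1]·ICC,

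and the actual two-sided error of a nominal 5% test is 2Φ(−1.96/√DE).

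Example, CV 0.8 and ICC 0.05: (1.64 × 3.71 − 1) = 5.08; DE = 1 + 5.08 × 0.05 = 1.254; √DE = 1.120; error = 2Φ(−1.75) = 8.0%.

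| Site ICC | DE, equal sites | Error | DE, CV 0.8 | Error | DE, CV 1.0 | Error |
|---|---|---|---|---|---|---|
| 0.01 | 1.027 | 5.3% | 1.051 | 5.6% | 1.064 | 5.7% |
| 0.02 | 1.054 | 5.6% | 1.102 | 6.2% | 1.128 | 6.5% |
| 0.05 | 1.135 | 6.6% | 1.254 | 8.0% | 1.321 | 8.8% |
| 0.10 | 1.271 | 8.2% | 1.508 | 11.0% | 1.642 | 12.6% |

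**Simulation of the fixed-pool model.** 20,000 trials per ICC with 445 subjects, 120 sites, 16 pools, site-size CV about 0.74, one time point, no covariates and no country variance. Model SE over true SE was 0.98 / 0.96 / 0.90 / 0.82 at ICC 0.01 / 0.02 / 0.05 / 0.10. Coverage of the 95% interval was 94.4% / 94.0% / 92.2% / 89.2%, that is, errors of 5.6% / 6.0% / 7.8% / 10.8%. At ICC 0, coverage was 95.1%, so the loss comes from the site effect. A separate simulation of 4,000 trials with similarly skewed sites gave errors of 6.2% / 8.6% / 10.9% at ICC 0.02 / 0.05 / 0.10.

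**The random-pool model.** The same 4,000-trial simulation gave errors of 4.6% / 5.5% / 5.8% at ICC 0.02 / 0.05 / 0.10. Adding a random site intercept within pool gave 4.2% / 4.8% / 4.3%. The primary specification is therefore close to nominal.

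**The case against.** Much of the case on the other side stands.

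- *The primary analysis is not harmed.* A reader might infer from the missing site term that the primary interval is too narrow as well. The figures do not support that: 4.6% to 5.8% error with the random pool. A small run of 150 trials per setting gave coverage near 93%, but its Monte Carlo margin is about ±1.96 × √(0.95 × 0.05/150) = ±3.5 points, so it adds nothing.
- *The fallback may never be used.* It needs non-convergence, and then it is one of two options. The other, variance components, does not make center fixed. The error rates above describe the fixed-center model if it is used, not the chance of using it.
- *The sensitivity text is redacted.* That its center effect is the pool is inferred from the only center effect the visible model defines. If the hidden text uses site or a robust SE, the point does not reach it.
- *The protocol leaves room.* Its primary-endpoint section and synopsis allow centre or region, and SAP 9 discloses the pooling with a reason. It would be too strong to call this a plain breach of the protocol; it is an unlisted choice that departs from 8.5.1.
- *The size is assumed.* The outcome is a self-completed score, analysed as change and adjusted for baseline score, age and EDSS, so the residual site ICC may be low. At 0.01–0.02 the effect is small.
- *The study is exploratory.* P-values are nominal and multiplicity is not controlled. That limits the consequences, but it does not excuse a single 95% interval that covers less than 95%, and such intervals are the main output of a single-arm study.

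What remains is that the SAP itself calls site clustering likely, and the fixed-center model as visible does nothing about it.

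**Conclusion.** The point holds for the fixed-center model only. The direction is certain for any positive site ICC; the size rests on an assumed ICC and site-size distribution. The two-sided error is about 5–6% at ICC 0.01–0.02, 6–9% at 0.05 and 8–12% at 0.10. The most uneven sites tried (CV 1.0) reach slightly beyond this, at 6.5% for ICC 0.02 and 12.6% for ICC 0.10. These figures also assume LS means at observed margins and treat the participating countries as fixed.

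The primary random-pool model needs no change on this ground. Nor does the Month 6 TSQM model: a reader might extend the point to SAP 14.2, but the only fallback stated there is variance components, with no fixed-center option.

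**What to change.** In SAP 14.1.1, state that whenever pooled center is fitted as fixed, as fallback or as sensitivity analysis, inference will use either standard errors clustered by study site (sandwich) or a random intercept for site within pooled center, keeping the planned within-subject covariance. If non-convergence is the reason for the fallback, prefer the sandwich SE, because another variance component could bring the same problem back. About 120 sites are enough clusters for it. The program must cluster on site and not on subject.

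In SAP 7, list the move from trial site (Protocol 8.5.1) to pooled center and give the reason.

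The cost is a few lines of SAP text and a small programming change, with no new data. Intervals become slightly wider. A random site term may be estimated at zero or again fail to converge.

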7.3.1 HRQoL

7.3.1.1 MSQoL-54

The MSQoL-54 questionnaire should be completed at Baseline and then at Months 12, and 24. The primary endpoint will be determined at Month 24 of this trial.

The MSQoL-54 is a multidimensional health-related quality of life measure that combines both generic and MS-specific items into a single instrument (Vickrey et al., 1995; Vickrey et al., 1997). The MSQoL-54 questionnaire was developed to measure HRQoL in subjects with MS. It is composed of 54 items, and is a combination of the SF-36 as well as an additional 18 disease-specific items such as fatigue and cognitive function. MSQoL-54 questionnaire (see [Appendix 2: MSQoL-54 SCALE](#)).

CCI

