The time difference between the start of the Course 1 Treatment Period and the start of the Course 2 Treatment Period will be calculated as follows:

- Relative Start of Treatment Course 2 (days) = Start of Treatment Course 2 - Start of Treatment Course 1 +1.

The Relative Start of Treatment Course 2 will be presented together with the number of subjects in the following groups for the SAF:

- Treatment Course 2 not started,
 - and discontinued before the Month 12 Visit,
 - and discontinued at or after Month 12 Visit
 - Lymphocyte count < 800 cells/mm³ at Month 12 Visit,
- Treatment Course 2 started,
 - and not delayed (see Section 9 for definition),
 - and delayed,
 - and any Lymphocyte count < 800 cells/mm³ at or after Month 12 Visit and before start of Treatment Course 2.
 - before / after Start of COVID-19 pandemic

The cumulative dose is defined as the sum of the number of tablets taken 10 mg divided by the weight for each treatment year:

- Cumulative dose = number of tablets taken in Treatment Course 1 * 10mg / weight in kg at Baseline + number of tablets taken in Treatment Course 2 * 10mg / weight in kg at Month 12b

The cumulative dose will be calculated only if the weight and number of tablets are available. Otherwise it will be missing. If the Treatment Course 2 wasn't started (i.e. no tablet taken in Treatment Course 2), the cumulative dose will be calculated only for the Treatment Course 1.

A subject data listing of the treatment compliance will be provided for the SAF.

14 Efficacy Analyses

The following sections describe the planned analyses for each efficacy endpoints.

For the detailed definition of covariates and stratification factors that are used in the statistical models see Section 9.

Descriptive summary statistics will be presented for the absolute values and the changes from baseline as applicable, for each visit and for all efficacy endpoints for the FAS. Details about the presentation of continuous and qualitative variables are given in Section 9.

Wherever possible, all estimated results from the statistical models will be calculated with the same observed margin which reflects the population of the whole corresponding analysis set, regardless of missing data.

14.1 Primary Endpoints: Changes in MSQoL-54 physical and mental health composite scores from Baseline to Month 24 Visit

The primary endpoints are the changes in MSQoL-54 physical and mental health composite scores at Months 24 Visit compared to Baseline.

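### The primary model has no Baseline-by-Visit term, so the Month 24 LS mean can be biased if the baseline slope differs by visit and missingness depends on baseline HRQoL

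*SAP*

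**What the plan says.** The MSQoL-54 schedule is set in Protocol 7.3.1.1: "The MSQoL-54 questionnaire should be completed at Baseline and then at Months 12, and 24". The primary model therefore has two post-baseline visits.

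In SAP 14.1.1 the outcome is defined by "Y represents change from baseline in MSQoL score" and the mean model by "X represents values of fixed effects including MSQoL score, age and EDSS at Baseline, and Visit (defined as a class variable". The analysis table in the same section, introduced by "Repeated mixed-effects linear model with the following adjusting factors", lists baseline score, age, EDSS in two classes, visit, and the two correlation terms. Neither place names an interaction. On covariance: "An unstructured covariance matrix will be assumed for the model".

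Two further statements matter. On missing data, the table says: "The repeated measurement model handles missing post-Baseline assessments under the assumption of missing at random". On the LS means, Section 14 says that model estimates will, where possible, be "calculated with the same observed margin which reflects the population of the whole corresponding analysis set, regardless of missing data", and 14.1.1 repeats that observed FAS margins apply, including the margin for the baseline composite score.

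The visible text says nothing on whether the baseline slope may change between visits or whether missingness is related to baseline score.

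**The concern.** With baseline score and visit as main effects only, a subject's expected change depends on baseline with the same slope at Month 12 and at Month 24. When everyone is observed this restriction does no harm to the LS mean at the average baseline. When Month 24 data are incomplete and the observed subjects differ at baseline from the whole FAS, the fitted slope carries the Month 24 estimate back to the FAS. A slope pooled over two visits is then the wrong one for Month 24 if the true slopes differ.

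Missing at random does not cure this. A likelihood analysis is protected under that assumption only if its mean model is right, and equal slopes are an unstated restriction on the mean model.

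At stake is the point estimate of both primary endpoints. In a single-arm trial the Month 24 LS mean is the whole primary result, and there is no control arm against which a shared bias could cancel. Some missing data are foreseen: Protocol 8.5.1 expects missing outcomes, and SAP Section 9 sets to missing the efficacy data collected after the Course 1 Treatment Period when Course 2 is delayed beyond the limit or never started.

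**Working it through.** **No plan figure to reproduce.** The sample-size section and its assumptions appendix are blacked out. Only N = 445, the two visits, the model terms, the FAS margins and the 0 to 100 scale come from the documents. Every SD, correlation, slope and missing rate below is an assumption. Month 12 is taken as complete, and age, EDSS and the center effect are left out.

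**Slopes.** The slope of change on baseline at visit t is

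slope(t) = r(BL,t) x SD(t)/SD(BL) - 1.

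With equal SDs, r = 0.75 and 0.55 give -0.25 and -0.45 (gap 0.20); r = 0.70 and 0.60 give -0.30 and -0.40 (gap 0.10).

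**Where the bias comes from.** Let d be the mean baseline of subjects observed at Month 24 minus that of all subjects, b the fitted common slope, s12 and s24 the true slopes, and k the regression of the Month 24 residual on the Month 12 residual. In large samples

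bias = -d x [(b - s24) + k x (s12 - b)].

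If s12 = s24, then b equals both and the bias is 0. If missingness is unrelated to baseline, d = 0 and the bias is 0. Both conditions are needed. With a steeper Month 24 slope and the worse-off at baseline missing, the sign is negative (improvement understated); reversing either one reverses the sign.

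Hand example: slopes -0.20/-0.40, equal residual SDs, within-subject correlation 0.6 (so k = 0.6), 20% missing, odds ratio 0.37 per baseline SD, d = 3.50, b taken midway at -0.30. Bias = -3.50 x (0.10 + 0.6 x 0.10) = -0.56. The full maximum-likelihood fit gives -0.60 in a large sample and -0.56 at N = 445.

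**Set 1: baseline SD 20, residual SD 14, within-subject correlation 0.6, N = 445, 1,500 trials.**

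| Slopes M12/M24 | Missing | Odds ratio per SD | Bias, common slope | 95% CI coverage | Bias with term | Coverage with term |
|---|---|---|---|---|---|---|
| -0.30/-0.30 | 20% | 0.37 | 0.04 (simulation error) | 94.6% | 0.04 | 94.6% |
| -0.25/-0.35 | 20% | 0.37 | -0.29 (0.41 SE) | 92.7% | 0.00 | 94.6% |
| -0.20/-0.40 | 20% | 0.37 | -0.56 (0.78 SE) | 88.7% | 0.03 | 95.3% |
| -0.20/-0.40 | 30% | 0.22 | -1.17 (1.53 SE) | 67.3% | -0.03 | 94.3% |

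In the large-sample runs, equal slopes with baseline-dependent missingness, and unequal slopes with missingness unrelated to baseline, both gave a bias of at most about 0.01 points.

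**Set 2: SD 18 at every visit, correlation between Months 12 and 24 of 0.70.**

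| r BL-M12 / BL-M24 | Missing at M24 | Log-odds of missing per SD | Bias, common slope | Bias with term |
|---|---|---|---|---|
| 0.70/0.60 | 10% | 0.35 | -0.05 | about 0 |
| 0.75/0.55 | 10% | 0.35 | -0.11 | about 0 |
| 0.70/0.60 | 22% | 0.35 | -0.11 | about 0 |
| 0.70/0.60 | 22% | 0.7 | -0.21 | 0.01 |
| 0.75/0.55 | 22% | 0.7 | -0.46 | -0.01 |
| 0.75/0.55 | 22% | 1.0 | -0.63 | 0.01 |

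At 22% missing and 0.7 per SD, the missing subjects average about 9 points, or half an SD, below the mean at baseline. The empirical SE in the fifth row is 0.89 with or without the term, so that bias is 0.46/0.89 = 0.5 SE.

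**Dependence on equal SDs.** Take r = 0.70/0.60, 22% missing and 0.7 per SD. If the Month 24 SD is 21, its slope is 0.60 x 21/18 - 1 = -0.30, the same as at Month 12, and the bias is 0. With a Month 24 SD of 20 it is -0.08.

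**The case against.** The strongest reply has five parts.

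- **Neither condition is documented.** A reader might infer that baseline-dependent missingness is enough to bias the result, or that correlation with baseline must fade over time and so steepen the Month 24 slope. The documents support neither. The first is contradicted by the equal-slope case. The second holds only if the spread stays about constant, and no visit-specific SDs or correlations are visible. This stands in full and is why the point is conditional.
- **The plan limits missing data.** SAP Section 9 maps an Early Termination assessment to the nearest planned visit lacking one, so a subject who leaves after Month 12 and attends that visit will usually fill Month 24. Protocol 5.5.1 and 5.5.2 keep subjects who stop the drug in scheduled assessments. Protocol 8.5.1 expects substantial delay of Course 2 in few subjects, and 5.5.1 links delay to lymphopenia or infection rather than to baseline HRQoL. This lowers the likely size. It does not help subjects who never start Course 2, because their later efficacy scores are set to missing even if they attend.
- **The list may not be closed.** The word before the listed effects leaves room for others, and text after the sexual-function rule in 14.1.1 is blacked out, so a sensitivity model with the interaction cannot be excluded. But the visible table of adjusting factors has no such term, and the primary model is what is at issue.
- **The study is exploratory.** SAP Section 9 and Protocol 8.5.1 say so. That limits what hangs on a p-value. It does not make a biased estimate acceptable.
- **The size is small.** Under weak dependence it is about a tenth of a point or less. This also stands.

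**Conclusion.** The visible primary model forces one baseline slope on Months 12 and 24 while standardising the Month 24 LS mean to the FAS baseline distribution. The missing-at-random statement does not protect that estimate if the slope differs by visit and Month 24 missingness depends on baseline HRQoL. If either condition is absent, there is no material bias.

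The illustrative size is -0.05 to -0.1 points at 10% missing with weak dependence, and -0.2 to -0.6 points at 22% missing with log-odds 0.7 to 1.0 per baseline SD and a slope gap of 0.1 to 0.2 under equal SDs. It exceeds one point only when both conditions are strong. All of this rests on assumed SDs, correlations and missing rates.

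A reader might go on to conclude that the primary result is invalid or that its type I error is inflated by a known amount. The documents do not support that. No rejection rate is offered here, because it would mix this bias with the separate question of how the standard error of the LS mean is calculated. This is a worthwhile, nearly free improvement to the primary model, not a fatal flaw.

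**What to change.** In SAP 14.1.1, add Baseline score x Visit to the fixed effects, in both the model equation and the table of adjusting factors, for the physical and the mental health composite. Keep the LS means at the same FAS margins.

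The cost is a change of SAP wording and one degree of freedom with 445 planned subjects. With equal slopes and 20% missing, the standard error moves only from 0.714 to 0.721. When the slopes are equal the term changes nothing material; when they differ it removes this bias. Age x Visit and EDSS x Visit could be added on the same reasoning, but they are optional and no calculation here supports them.
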